7.6 Data management

Data extraction and elaboration is done locally and pooling of aggregated data is done on a remote research environment (see [Figure 7-2](#) for overview).

Figure 7-2 Model for data sharing and elaboration

Due to the different database characteristics and coding schemes it is not possible to use one single data extraction algorithm for all the databases. To reconcile differences across terminologies a shared semantic foundation will be built for the definition of events under study by selecting disease concepts from the Unified Medical Language System (UMLS, and set up a multi-step and iterative process for the harmonization of event data ([Trifiro et al 2014](#)). The sequential steps of this process are shortly described below:

All events/outcomes and covariates will be ascertained using a list of agreed ICD (UK, Denmark, Italy, Netherlands, and Spain), ICPC (Netherlands) and READ (UK) codes. The proposed lists of codes will be created following a number of steps:

1. Case definition
2. Preliminary list of concept identifiers using codemapper to UMLS Metathesaurus Browser

3. Addition of codes found after literature review of validated lists of codes for each of the study outcomes in each of the databases; and
4. Consensus with partners involved in the management and analysis of each of the data sources. As coding might change over time, relevant codes might be updated during the course of the project.

Identification of Unified Medical Language System® (UMLS®) concepts

A UMLS concept is identified by a Concept Unique Identifier (CUI) and describes a single medical notion that can be expressed using different synonyms (terms). For each event, a medical definition will be created and, based on such definition relevant UMLS concepts are identified and projected into the database-specific terminologies. In addition, for those databases where free text is available, the labels of the codes are considered for free text search of the events.

Definition of data extraction algorithm

Based on the relevant diagnostic codes and key words (for free text search), a data extraction algorithm will be constructed for each event based on the consensus of the data providers. This data extraction algorithm will then be implemented by all databases.

Event data extraction

Subsequently, each database extracts data locally and transforms them into a simple common data model, i.e. standardized patient, drug and event files linkable via a patient unique identifier.

Data elaboration

A standardized Jerboa[®] script and instructions will be created by [REDACTED] to create the study specific output tables. This will be double coded in SAS (version 9.4) by [REDACTED].

7.6.1 Missing data

Since the underlying data represent attended medical care we assume that absence of information of clinical events means absence of that condition. Lack of information on smoking, and alcohol use may occur, but this is unlikely differential.

7.6.2 Data sharing

A study-specific folder on the central Octopus remote research environment (RRE) for secure access by members will be used to analyze the output provided by Jerboa[®]. These output files will contain only anonymized de-identifiable data that will be shared in the RRE where members will have a secure and restricted access and where data will be analyzed. SAS, version 9.4 (SAS Institute Inc., Cary, NC), will be used for post-processing of data.

7.7 Data analysis

All analyses will be performed at the [REDACTED] the scientific lead for this multi-database study, in close collaboration with [REDACTED], the coordinating centre for the study. Data will be deposited in the remote research environment and participating partners can inspect the analysis by remotely accessing.

Below the main statistics are described, a detailed SAP will be prepared after PRAC/CHMP endorsement of the protocol.

7.7.1 Analyses timing

Yearly progress reports will be submitted with a first report based on 2016 data to be expected in Q1 2018.

These progress reports will include the following information:

- Size of the study base and exclusions
- Number and % of LCZ696 users
- Number of cases for each of the primary outcomes of interest

7.7.2 Final analysis

The final analysis based on validated cases will be conducted at the end of the study (after reaching the necessary number of cases) and is expected to be submitted in Q2 2020.

7.7.2.1 Attrition diagram

Reasons for exclusion of cases and controls will be described with a detailed attrition diagram.

7.7.2.2 Demographic and baseline characteristics

Demographic and clinical characteristics of case and control patients at the index date of the case-control analysis will be described separately for each outcome of interest using contingency tables for categorical variables and mean, standard deviation (sd), range, median and interquartile range (IQR) for continuous variables in each individual database.

7.7.2.3 Primary and secondary analyses

Conditional logistic regression analyses will be used to estimate crude and adjusted relative risks (expressed as odds ratios [ORs]) of each specific outcome with corresponding 95% confidence intervals (CIs).

The primary analysis is current LCZ696 and statin versus current use of statin (any dose) without current use of LCZ696.

Secondary analyses comprise investigation of dose of statin and duration of LJC696, recent use of LJC696 or statins, and individual statins. In the dose specific analysis for statins the reference category will be current low dose of statins and non-use of LJC696.

7.7.2.4 Confounding

Control for confounding will be based on matching and matched analyses plus adjustments based on the change in estimate method as proposed by [Maldonado and Greenland \(1993\)](#) per database.

7.7.2.5 Sensitivity analyses

Sensitivity analyses that focus on the limitations will be conducted and described in the SAP, this comprises evaluation of the effect of missing first prescriptions of LCZ696.

7.7.2.6 Handling of missing values/censoring/discontinuations

No imputations will be done.

7.7.2.7 Pooling

All estimates will be calculated by database and pooled. The adjusted odds ratios estimated with the logistic regression model in each database will be combined in a two-stage meta-analysis using a fixed-effects model and a random-effects model employing the DerSimonian and Laird method ([DerSimonian and Laird 1986](#)). Given the poor performance of the significance tests for statistical heterogeneity no such testing will be used. Rather, the estimates will be presented as outcomes of the fixed and random effects model respectively. In addition, to optimize power, we will conduct a one-stage model, that will estimate the effects putting all individual level data together while accounting for the matching of cases and controls. One-stage meta-regression may also be used to investigate the sources of heterogeneity and adjust for structural differences between the data sources when appropriate.

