7.5 Study size/power calculation

The sample size is calculated following a non-inferiority approach (Wang and Chow 2007), with the intent to demonstrate that the increased risk due to LCZ696 exposure is less than 3-fold for hepatotoxicity and less than 5-fold for myotoxicity or acute pancreatitis.

Forty cases with hepatotoxicity will allow ruling out a 3-fold increased risk with a one-sided test (80% power, 5% type I error), assuming a conservative case:control ratio of 1:4 and conservatively, that 20% of the statin-exposed HF patients concomitantly use LCZ696 in the control group (Table 7-6).

Assuming an incidence rate of acute hepatic events in statin-treated HF patients of 6.1 and 12.9/10,000 PYs (Cziraky et al 2006), the underlying study base is expected to be comprised of at least about 66,000 and 31,000 patient-years (PYs), respectively.

A total of 19 cases with a myotoxic event will allow ruling out a 5-fold increased risk (Table 7-6). Assuming IR of myopathy in statin-treated HF patients between 2.3 and 9/10,000 PYs (Macedo et al 2014), the underlying study base should comprise of at least about 83,000 and 21,000 PYs, respectively.

The underlying study base should comprise of at least about 38,000 PYs in order to observe 19 cases of acute pancreatitis assuming an IR of statin-associated acute pancreatitis of 5/10,000 PYs (Kuoppala et al 2015).

Table 7-6 Sample size scenarios for a one-sided non-inferiority test (80% power, 5% type 1 error)

[figure not shown]
Risk to be ruled out	No of cases needed	
	with 10% LCZ696 use	with 20% LCZ696 use
5	33	19
3	71	40

Risk to be ruled out	No of cases needed	
	with 10% LCZ696 use	with 20% LCZ696 use
2	179	100

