7.10 Other aspects

Not applicable.

8 Protection of human subjects

For this study, participants from various EU member states will process personal data from individuals which is collected in national/regional electronic health record databases. Due to the sensitive nature of this personal medical data, it is important to be fully aware of ethical and regulatory aspects and to strive to take all reasonable measures to ensure compliance with ethical and regulatory issues on privacy.

All of the databases used in this study are currently already used for pharmacoepidemiological research and have a well-developed mechanism to ensure that European and local regulations dealing with ethical use of the data and adequate privacy control are adhered to.

According to these regulations, rather than combining person level data and performing only a central analysis, local analyses will be run, which will generate anonymized data with less detailed information that will be pooled across databases.

The output files are stored in the central Remote Research Environment (RRE) of the [REDACTED]. These output files do not contain any data that allow identification of subjects included in the study. In fact, each record is completely anonymous and does not contain any identifier key. Starting from this, the RRE implements further security measures in order to ensure a high level of stored data protection, according to the article 34 of legislative decree 196/2003 and article 22 of Regulation (EC) 45/2001.

The protocols will be reviewed by the governance boards of the respective databases. As this is a non-interventional study, there is no need for ethical approval in the Netherlands, UK, Denmark and Italy. For SIDIAP (Spain), both the scientific committee for SIDIAP studies and the local ethics committee will evaluate the protocol before the study can be carried out.

Regulatory and ethical compliance

This study was designed and shall be implemented and reported in accordance with the Guidelines for Good Pharmacoepidemiology Practices (GPP) of the [International Society for Pharmacoepidemiology \(2008\)](#), the STROBE (Strengthening the Reporting of Observational Studies in Epidemiology) guidelines ([Vandenbroucke et al 2007](#)), and with the ethical principles laid down in the Declaration of Helsinki.

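### At the planned 19 or 40 cases, two-stage pooling of database odds ratios falls well short of the stated 80% power; the one-stage model already planned should be named primary

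*Protocol*

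**What the plan says.** Section 7.5 of the protocol sets the aim as showing that the increase in risk is "less than 3-fold for hepatotoxicity and less than 5-fold for myotoxicity or acute pancreatitis". It sizes the study by the total number of cases, with a one-sided 5% test and 80% power, "assuming a conservative case:control ratio of 1:4 and conservatively, that 20% of the statin-exposed HF patients concomitantly use LCZ696 in the control group". This gives 40 cases for hepatotoxicity. For the 5-fold margin, "A total of 19 cases with a myotoxic event will allow ruling out a 5-fold increased risk", and acute pancreatitis has the same number. Table 7-6 also has a column "with 10% LCZ696 use", with 71 and 33 cases for the 3-fold and 5-fold margins.

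Section 7.7.2.7 first describes the two-stage route: "The adjusted odds ratios estimated with the logistic regression model in each database will be combined in a two-stage meta-analysis", with fixed-effects and DerSimonian-Laird random-effects results both shown. It then adds: "In addition, to optimize power, we will conduct a one-stage model, that will estimate the effects putting all individual level data together", with the matching accounted for. It does not say which pooled result decides the rule-out, or what happens to a database whose odds ratio cannot be estimated.

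Section 7.6 speaks of pooling aggregated data. Section 8 says that, "rather than combining person level data and performing only a central analysis, local analyses will be run", and that these produce less detailed anonymised data for pooling. Section 7.6.2 says that anonymised output files are shared and analysed in the remote research environment.

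**The concern.** The sizing treats all cases as one data set, whereas the method listed first fits five separate models and combines five log odds ratios by inverse variance. With 20% use and no effect, 40 cases contain about 8 exposed cases and 19 cases about 4. A database with no exposed case has a conditional maximum-likelihood log odds ratio of minus infinity and no usable standard error, so it cannot enter inverse-variance pooling. Unless another handling is specified, its cases are lost, and they are lost because its data point away from harm.

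Two things are at stake. A safety rule-out that should succeed four times in five would fail much more often, with an odds ratio that looks raised when there is no effect. And three pooled results (fixed, random, one-stage) are planned with none named primary, although they can give different answers to the same rule-out question.

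**Working it through.** **Inputs from the protocol.** Section 7.5: one-sided 5%, 80% power, margins 3 and 5, case:control ratio 1:4, LCZ696 use 20% (alternative 10%). Table 7-5: five databases of 1.2, 5.7, 1.8, 1.5 and 5.1 million, together 15.3 million.

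**Assumptions, not in the protocol.** True odds ratio 1; the same uptake in every database; cases split either equally or in proportion to database size; a database without a finite estimate is left out of the pooling; no covariate adjustment.

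**Step 1: the plan's own figures.** With true odds ratio 1,

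n = (1.645 + 0.842)² / ln(margin)² × (1 + 1/4) / [p(1 − p)].

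- p = 0.20: margin 3 gives 40.02, margin 5 gives 18.65, margin 2 gives 100.53.
- p = 0.10: 71.15, 33.15 and 178.72.

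Table 7-6 has 40, 19, 100 and 71, 33, 179, so it is reproduced to within one case. It is a calculation for one pooled data set.

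**Step 2: databases with no exposed case.** For a database with share s of the cases, the chance of no exposed case is (1 − p·s)^n.

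- Equal split, 40 cases: 0.96^40 = 0.195, times 5 = 0.98 databases.
- Equal split, 19 cases: 0.96^19 = 0.460, times 5 = 2.30.
- Size-proportional, 40 cases (database order as above): 0.531 + 0.045 + 0.386 + 0.453 + 0.063 = 1.48.
- Size-proportional, 19 cases: 0.741 + 0.230 + 0.636 + 0.686 + 0.270 = 2.56.

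**Step 3: simulated rule-out.** Several thousand studies per setting. Two-stage: conditional logistic fit per database, then inverse-variance pooling. One-stage: one conditional logistic fit on all matched sets. Success means that the one-sided 95% upper limit lies below the margin. Ranges cover both splits and repeated simulations.

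| Cases, use, margin | Two-stage fixed: median OR | Two-stage fixed: margin excluded | One-stage: margin excluded |
|---|---|---|---|
| 40, 20%, 3 | 1.20–1.27 | 56–64% | 82–85% |
| 19, 20%, 5 | 1.4–1.6 | 36–49% | 82–85% |
| 71, 10%, 3 | 1.27–1.38 | 47–58% | 84–86% |
| 33, 10%, 5 | 1.6–1.9 | 25–40% | 82–84% |

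The one-stage median odds ratio is 1.00 in each row. DerSimonian-Laird pooling does slightly worse than fixed-effect: about 54–58% with 40 cases and 35–46% with 19. The fixed-effect and one-stage verdicts disagree in about 22–29% of studies with 40 cases and 38–50% with 19.

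**Step 4: checks on the result.**

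- More controls do not cure it. With 20 per case (assumed, since Section 7.2.2.4.1 matches all available controls), two-stage success is 62–70% (40 cases) and 37–55% (19 cases), against 91–94% one-stage.
- With the true odds ratio at the margin, the upward bias is gone: median 2.83–2.90 for a true 3, and 3.52–3.86 for a true 5. The two-stage false rule-out rate is then about 4% (40 cases) and 6% (19 cases), near the nominal 5%.
- More cases reduce the loss. With 51 cases and margin 3, two-stage success is about 75–79%.

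**The case against.** The strongest reply is that the protocol already plans the better analysis. The one-stage model stands in the same section, is there expressly for power, and keeps the stated power in every row of the table. Nothing calls the two-stage result primary. This stands, and it makes the point one of ranking the analyses, not of a missing analysis.

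Second, 19 and 40 are minimum counts, and one study base serves all three outcomes. If it reached the largest requirement in Section 7.5, 83,000 patient-years, the section's own rates would give 83,000 × 5/10,000 ≈ 42 pancreatitis cases and 51 to 107 hepatotoxicity cases (6.1 to 12.9 per 10,000). Two-stage success would then be about 94–96% (42 cases, margin 5), 75–79% (51, margin 3) and 99% (107, margin 3). This also stands as a limit on the size of the problem. But Section 7.7.2 ties the final analysis to reaching the necessary number of cases, and Section 7.9 calls uptake the main uncertainty, so the plan should work at its own planning numbers.

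Third, handling of zero cells commonly belongs in the SAP, which is not shown. For that reason its absence is treated here as an assumption of the calculation, not as a fault. The order of the pooling methods and the lack of a primary result are in the protocol itself.

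A reader might infer more than the documents support:

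- That most databases will have no exposed case. This is untrue at 40 cases and 20% use (1.0 to 1.5 of 5) and only about half at 19.
- That two-stage pooling cannot work at all. Some two-stage estimate exists in about 97% or more of simulated studies at 20% use.
- That the pooled odds ratio is always biased upward. That holds near an odds ratio of 1, not at the margins.
- That Section 8 forbids a one-stage fit. It rejects a purely central analysis of person-level data, and Section 7.6.2 provides for anonymised files to be analysed in the shared environment.

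**Conclusion.** The point holds in this limited form. At the case numbers in Section 7.5, the pooling method listed first in Section 7.7.2.7 reaches about 56–64% (40 cases) or 36–49% (19 cases) instead of 80%, and about 47–58% or 25–40% at the 10%-use sizes of 71 and 33. Under no effect its odds ratio is pushed up by about 20–27% with 40 cases and 40–63% with 19. The error lies in failing to rule out a risk that is not there; the false rule-out rate stays near nominal.

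The result rests on a true odds ratio of 1, a common uptake, an equal or size-proportional split, and the dropping of databases without a finite estimate. Covariate adjustment was not simulated; fitting adjusted models per database, as Section 7.7.2.4 foresees, would make sparse fits worse. Because verdicts differ between methods in roughly a quarter to a half of studies at the planned sizes for 20% use, leaving the primary result unnamed matters for the conclusion of the study.

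**What to change.** In Section 7.7.2.7, name the one-stage conditional logistic model, with strata formed by matched set within database, as the primary analysis for the rule-out. State that exact or Firth-penalised limits are used when exposed cases are few. Keep the two-stage fixed and random results as a descriptive display and for looking at heterogeneity, and say how databases with no finite estimate are shown there.

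Align Sections 7.6 and 8 with this by stating that anonymised matched-set records are shared in the remote research environment. If only the unadjusted fit has to be supported, tables of exposure by matched set are enough, because they give the same conditional likelihood.

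The cost is wording in three sections and possibly one change to the shared output file. No new data and no change of design are needed.

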7.8 Quality control

The study will be conducted according to the guidelines for Good Pharmacoepidemiology Practice (GPP) ([International Society for Pharmacoepidemiology 2008](#)) and according to the ENCePP code of conduct ([European Medicines Agency 2011](#)). All database partners have experience in conducting pharmacoepidemiological research and research is done by researchers trained in pharmacoepidemiology. In addition; the databases are representative of the respective countries and database specific disease prevalence rates are in line with what has been published before.

All programs will be programmed according to agreed coding standards and will be validated by double programming or source code review with second programmer involvement. Only validated software (SAS version 9.4, SAS Institute Inc., Cary, NC) will be used for the statistical analyses.

7.9 Limitations of the research methods

The limitations of this study will be mainly due to the availability and level of detail of data. Not all potential confounders (e.g. life style factors such as smoking and alcohol use; or body mass index [BMI] which is a very dynamic variable and which is not well recorded or not recorded at all) are contained in (all) databases, this may lead to residual confounding.

Information on the prescribed dose and duration of a prescription is not contained in all databases and has to be estimated, which might lead to some misclassification of exposure, however, we do capture recency of exposure and can explore the effects of dose in PHARMO and CPRD which will allow us to assess the extent of this effect. Since LCZ696 may be prescribed by specialists initially we may misclassify exposure if it is not recorded in the databases. This would attenuate an effect since it is likely to be non-differential; a sensitivity analysis will be planned to address this.

All of the databases, apart from the Aarhus University Prescription Database and PHARMO, have information on prescription only and not on dispensing. None has information on actual drug intake. This implies that we do not know whether the patient actually took the drug – however, this may be non-differential leading to underestimation of risk.

Misclassification of endpoints as well as confounders is possible. For the different databases that will be used, validation studies have shown that coding is reliable in the databases and that these databases are suitable for pharmacoepidemiological research. For those databases where free text is available (PHARMO, HSD, CPRD and SIDIAP), validation of endpoints will be conducted and comparison of incidence rates of endpoints among databases in the quality run will allow checking for internal and external validity. Laboratory measurements will be needed for case finding/validation and the availability of these data will vary across the databases. The amount of misclassification of the outcome may differ between databases due to differences in availability of validation data or laboratory confirmations. However, since cases and controls are sampled and analyzed within the same database, misclassification will be similar for matched cases and controls in the same database. Bias due to misclassification of the outcomes may just differ between the databases.

For all databases, apart from Aarhus University Prescription Database, it should be noted that the primary aim of data collection is patient management and not medical research. This implies that only events are collected which are deemed to be relevant to the patient's care. In addition, specialist information is incomplete in the majority of the databases. Aarhus and PHARMO contain all reimbursed prescriptions from GPs and specialists. The other databases are primary care databases, so they may not capture all prescriptions of specialists. However, in all of these countries (UK, Italy, and Spain), the GP is the gatekeeper of care and prescriptions initiated by the specialist are continued by the GP. Missing information on LCZ696 exposure may lead to some misclassification of duration in the secondary analyses.

None of the databases will be able to capture over-the-counter (OTC) drug use. This may be relevant for instant with respect to use of acetaminophen in the context of hepatotoxicity, as most acetaminophen use will be OTC and prescription use will be limited.

Finally, there are differences in timing of data updates in the various databases (medical records are continuously updated, administrative databases are updated only once per year in most instances). However, as data-extraction will be repeated during the course of the study, this should allow for “up-to-date data” at study end.

The most important uncertainty is about the uptake of LCZ696, which may limit the power of the study.

